Protocol Elements Checklist for:

Single-dose Intraoperative Methadone for Early Ambulation and Sustained Pain Control in Spinal Fusion Surgery Patients

1) Background/Significance

Methadone is a synthetic opioid analgesic with agonist properties at the μ -opioid receptor binding site that has long been used as an alternative to morphine and hydromorphone in patients with severe pain. It has a diffuse bioavailability and is highly efficacious through its oral form, yet its bioavailability is heavily dependent on variability in cytochrome P450 3A4 activity, and is quite variable amongst individuals. Methadone reaches peak plasma concentrations in 2.5 to 4 hours after oral administration, has a rapid onset, has a half-life is between 20-35 hours (range 5-130 hours), and analgesia may be reported for up to 108 hours after a single dose. Repeated dosing during this interval may result in drug accumulation and an increased risk of adverse reactions.

Methadone has an asymmetric carbon skeleton with two carbon side chains which allow for two enantiomeric forms, the D- and L-isomers, and while the racemic mixture is administered, only the L-isoform seems to have clinical activity. The binding of the D-isomer, while not implicated in pain control may influence opioid potentiation and tolerance by binding to the NMDA receptor. Methadone's NMDA receptor site antagonism acts to inhibit enzymes such as adenyl cyclase and their downstream production of secondary signaling molecules like cyclic AMP. This activity may attenuate opioid tolerance and opioid abstinence syndrome as NMDA receptor agonism has been implicated in the development of hyperalgesia, acute and chronic tolerance, and chronic pain states. Its antagonisms may explain the low rate of dependence seen with methadone.

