In another series of spinal fusion patients administered 20mg methadone intra-operatively and 5mg doses as needed post-operatively in the recovery room (1-3 doses), there was little variability in methadone blood concentration in patients with adequate pain control, suggesting a dose-dependent effect.8 Mean half-life was 21±13hours with a range of 5-48 hours, with a VAS rating of 1.5±1.3 with adequate pain control. A repeat dose of methadone (i.e. 2.5, 5, or 10 mg iv) in the recovery room provided sufficient pain control for the remainder of the hospitalization for some patients in this cohort. The 2.5mg dose was associated with an average additional 7.4h of pain control, while the 5 and 10mg doses were associated with 9.6h of pain control. In another study cited in this report, 40% of surgical patients required no additional post-operative pain control after a single 20mg iv methadone dose intra-operatively, and the 35% that did require a single additional dose required it on average 18.4±6.6 hours post-operatively. The remainder received additional non-narcotic pain medications post-operatively which were sufficient to control pain to tolerable levels.

In one of the first series of methadone use in patients undergoing lumbar fusion surgeries, 22 patients were divided into two treatment arms with one group of patients receiving methadone only and the other receiving methadone plus ketamine.⁵ While there was no difference in pain rating post-operatively, the ketamine plus methadone group used significantly less methadone (70%) than the other control groups. This finding suggests that intra-operative co-administration of ketamine may potentiate the effects of methadone. To keep consistent with this data and to demonstrate a narcotic minimizing plan that sufficiently controls patients' pain, ketamine will included in this proposed protocol, as it is already a medication used for the analgesia of patients undergoing this surgical procedure.

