Age <21 or >80, renal failure requiring dialysis or serum creatinine greater than 2.0, significant hepatic dysfunction (liver function tests greater than twice the upper limit), hepatic cirrhosis, pulmonary disease requiring home oxygen therapy, obstructive sleep apnea, severe heart disease, allergy to methadone, morphine, ketamine or fentanyl, **recent or distant history of opioid abuse,** opioid use equal to or greater that the equivalent of 10mg morphine per day, poorly managed psychiatric illness, a known history of alcohol abuse, morbid **obesity (for the purposes of this study body mass index > 50 kg/m2),** treatment with other NMDA receptor antagonists, HIV-1 protease inhibitors, erythromycin or ketoconazole, prolonged QTc on pre-operative EKG, and the refusal or inability to sign the consent form to agree to participate in this study.

State primary and secondary outcome(s)

The primary outcomes for the study include total narcotic dose post-operative, frequency of narcotic use, the time to first ambulation after surgery with PT, length of stay, disposition (i.e. level of rehabilitative care), and improvement on clinical questionnaires in the intervention group as compared to the control group. Secondary outcomes include better subjective pain control, need for post-operative course of

dexamethasone for post-operative/post-fusion radiculopathy or neurapraxia/neuropathy and fusion at 3-6 months.

> For Randomized clinical trials

• Indicate whether a parallel or crossover study, and the number of treatment groups
The study will take the form of a parallel, 2 arm analysis of a methadone treatment group or a
group receiving the current standard of care without intra-operative methadone administration.

• Describe randomization and blinding procedures

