case and will administer a 0.2 mg/kg single-dose administration of methadone on incision (not to exceed 20 mg, as used in the literature) with a ketamine infusion of 4 µg/kg/min and a remifentanil infusion starting at 0.1 µg/kg/min and titrating to effect or sufentanil infusion starting with a dose of 0.3 µg/kg/hr and titrating to effect. These standard doses have been well documented and studied in the literature as demonstrated above and will be overseen and have been approved by board certified anesthesiologist. For lengthier procedures, there will not be re-dosing of narcotics toward the end of the procedure. The operative procedure will not be altered in any way for the purposes of this study, and is beyond the scope of this protocol, yet can be detailed as requested. The patient will be taken to the recovery room postoperative and will be put on a standard post-operative morphine PCA as used in our department at a rate of 1mg per 6 minute lock-out period. This standard dose and therapy has been used in nearly all postoperative lumbar fusion patients to date. Patient's narcotic usage and pain rating will be recorded at the intervals listed above and when stable from a cardiovascular standpoint, will be transition to the neurosurgery floor. Once able to bare weight, the patient will be encouraged to work with physical and occupational therapy as per standard post-operative protocol. One the patient uses the PCA at a rate of less that once an hour, and can be managed with oral pain medications, the PCA will be removed. The remainder of their post-operative care will be according to the standard departmental protocol, and when milestones such as ambulation, voiding, and pain control are met, they will be discharged either to home, an acute care facility, or a subacute rehabilitation center. Per standard of care, the patients will return to the clinic at 2 weeks and 3 months as part of their routine clinical care. Any adverse events/reactions will be recorded and managed as normally they would be, and naloxone will be available for suspicion of narcotic overdose. Patient assigned to the control group will be monitored in the manner post-operatively, as is the standard of care for all of our patients.

Define the outcome measures pertaining to each aim.

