Two sample T-tests will be performed to evaluate continuous variables such a total morphine dose, pain level per VAS, time to first morphine dose, time to ambulation, and time to discharge. The assistance of a statistician, [name], from the Albert Einstein College of Medicine, Division of Biostatistics will be used for statistical analyses performed in this study. Wilcoxon Rank Sum Test will be used if outliers are noted in the study population, detected as more than 5 MAD from the median, and a concern presents that single patients may skew the data. Additionally, review of these patients who are outliers may also necessitate their exclusion from this work if they provide data that will significantly modify the mean of the remaining patients. This can be accounted for in the goal of 60 patients to be accrued in each arm of the study. A thorough explanation and review will performed on any such patients in any form of write up of this work.

At least one study hypothesis (or a statement that the study is hypothesis-generating or a feasibility study):

The use of single dose intraoperative methadone will decrease total narcotic usage, time to ambulation, mean pain rating at 24 and 48 hours and will decrease number of days of hospitalization compared to sufentanil (current standard of care) controls.

• A statement regarding specifically what data are to be used to test the hypothesis (or to generate the hypotheses)

We will obtain data of total narcotic usage, days until patients ambulate with physical therapy, pain ratings at 24 and 48 hours, and days to discharge, all obtained from the patient's medical record.

- o The statistical method(s) to be used to test the hypothesis with that data
 Two-sample T-test will be used with the assistance of an Albert Einstein statistician, [name], to analyze
 the above data and determine if there is statistical significance between the two groups, in addition to the
 stipulations outlined above to address outlier patients.
- A power analysis to determine the sample size (even for pilot studies)

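### The hypothesis claims lower total narcotic usage, but the outcome as defined is post-operative opioid, so on that reading the methadone study dose and the infused opioid are not counted

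*Combined protocol and SAP*

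**What the plan says.** The hypothesis in section 7 (Data Analysis) reads: "The use of single dose intraoperative methadone will decrease total narcotic usage, time to ambulation, mean pain rating at 24 and 48 hours". It does not restrict the opioid count to the post-operative period. The data statement just below it is equally open: "We will obtain data of total narcotic usage, days until patients ambulate with physical therapy, pain ratings at 24 and 48 hours". Neither gives a time window, a list of opioids or a common unit. The sample-size text in section 3 and the data-collection paragraph in section 2 also speak of overall narcotic usage without defining it.

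The outcome definition in section 2 is narrower: "The primary outcomes for the study include total narcotic dose post-operative, frequency of narcotic use, the time to first ambulation after surgery with PT". The methods paragraph of section 7 names the variable to be tested: "Two sample T-tests will be performed to evaluate continuous variables such a total morphine dose, pain level per VAS, time to first morphine dose". In the planned-interventions paragraph, morphine is the drug in the post-operative PCA, and narcotic usage is described as recorded after the patient reaches the recovery room.

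The intervention is itself an opioid: "0.2 mg/kg single-dose administration of methadone on incision (not to exceed 20 mg, as used in the literature". The randomization paragraph says it is added to fentanyl and ketamine. The planned-interventions paragraph pairs it with a remifentanil or sufentanil infusion titrated to effect. The outcome-measures paragraph says that care is otherwise the same in both arms.

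Section 6 (Risk/Benefit) words the hypothesis more narrowly, as a reduction in post-operative narcotic usage.

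**The concern.** The claim and the measurement are different quantities. If the test is run on post-operative opioid, the count omits the component that the randomization changes. A patient who receives methadone at incision and then draws correspondingly less morphine from the PCA has the same peri-operative exposure, yet scores as a reduction.

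The conclusion is what is at stake. Less post-operative opioid is a legitimate and useful finding. Lower total narcotic usage is a broader claim, and the outcome as defined cannot show it. A significant result, reported against the hypothesis in section 7, would say more than was measured.

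**Working it through.** **1. The plan's own figure.** The sample size reproduces. For a difference of 0.56 SD, two-sided alpha 0.05 and 80% power, n per group = 2 × (1.96 + 0.84)² / 0.56², which rounds up to 51, as stated. With 60 per arm, power = Φ(0.56 × √(60/2) − 1.96) = Φ(1.11), about 86.6%. The point does not touch the sample size.

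**2. Side by side.**

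| Place | Quantity | Study dose counted? |
|---|---|---|
| Section 7, hypothesis | total narcotic usage | not defined |
| Section 7, data statement | total narcotic usage | not defined |
| Section 3, sample-size text | overall narcotic usage | not defined |
| Section 2, primary outcomes | post-operative narcotic dose | no, given at incision |
| Section 7, t-test variable | total morphine dose | no, not morphine |
| Section 6, hypothesis | post-operative narcotic usage | no, given at incision |

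The only places that say what is counted point to post-operative opioid. No place adds an intra-operative opioid to the outcome or gives a conversion.

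**3. What is left out.** Study dose D = min(0.2 mg/kg × weight, 20 mg): 10 mg at 50 kg, 14 mg at 70 kg, and 20 mg from 100 kg upward. The infused and bolus opioid of both arms is also left out; the control doses are not stated.

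**4. The net effect.** Let r be mg of morphine equivalent per mg of methadone. The between-arm change in total opioid is

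Δtotal = Δpost-operative + Δother intra-operative + D × r.

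A post-operative count estimates the first term only. The documents give D but not r, no mean or SD for post-operative use, and no control intra-operative dose. Neither the size nor the sign of Δtotal can be obtained from them.

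**5. Illustration, not an estimate.** Assume pure displacement (Δtotal = 0), equal other intra-operative opioid, and r = 1. The post-operative count then falls by D mg with no change in total. Power = Φ((D/SD) × √30 − 1.96), with 60 per arm and an assumed SD of post-operative use:

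| D | SD 25 mg | SD 40 mg | SD 60 mg |
|---|---|---|---|
| 14 mg | 87% | 48% | 25% |
| 20 mg | 99% | 78% | 45% |

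These are chances of a significant post-operative reduction when total opioid has not changed. Both r and the SD are assumptions.

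**The case against.** The strongest reply is that this is loose wording. The primary outcome is labelled post-operative, section 6 states the hypothesis in the same terms, and post-operative opioid is an accepted endpoint that suits the protocol's interest in PCA use and early mobilisation. That stands, and it is why the first part of the fix is only a matter of wording. It does not remove the mismatch, because the formal hypothesis in the analysis section is still the broader one.

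A reader might infer several stronger things that the documents do not support:

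- **That the plan excludes the study dose outright.** No sentence says so. Exclusion follows from the outcome label and the morphine variable, and the latter is given as an example. The total usage to be taken from the medical record is undefined and could be read more widely.
- **That a lower PCA total is close to guaranteed.** The Background cites a paediatric scoliosis series in which lower PCA use after intra-operative methadone was not statistically significant. The illustration above also ranges widely.
- **That methadone acts throughout the counted period.** The Background says "analgesia may be reported for up to 108 hours after a single dose", but this is an upper limit in a sentence that begins with oral administration. The same section reports a mean half-life of 21 ± 13 hours, and a further dose needed at a mean of 18.4 ± 6.6 hours in some patients.
- **That total opioid rises once the study dose is counted.** This needs assumed control use, an assumed conversion and equal infused opioid, although the infusions are titrated and methadone may reduce them. Nor can the cited 40% reduction be used safely: the caesarean series calls it overall consumption, so subtracting methadone from it may count the drug twice.
- **That the Background and objectives make the total claim too.** The phrase "to demonstrate a narcotic minimizing plan" explains why ketamine is included, and the objectives say only that narcotic usage will be lower.

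**Conclusion.** The point holds in this form. The section 7 hypothesis is about total narcotic usage, while the outcome and the named test variable are post-operative. Tested that way, a positive result supports only a reduction in post-operative opioid. What is certain is the mismatch, together with an uncounted study dose of 0.2 mg/kg up to 20 mg if the post-operative reading is the intended one. If the wider reading was meant, the outcome definition and the test variable need correcting instead, and conversions are missing. Either way the passages must be reconciled. The size and sign of the net peri-operative effect remain unknown. The endpoint, the sample size and the randomized comparison of post-operative opioid are not called into question.

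**What to change.** 1. Reword the section 7 hypothesis, and the matching overall narcotic usage in the section 3 sample-size text, to post-operative narcotic usage, in line with the primary outcome in section 2 and the wording in section 6. Limit the opioid conclusion to that.
2. Add one pre-specified supporting analysis of total peri-operative opioid in both arms: methadone study dose, intra-operative infused and bolus opioid, and post-operative opioid, taken from the anaesthesia record and the chart. State a morphine-equivalent conversion for every opioid in the sum, with a low-to-high range for methadone. Claim lower total narcotic usage only if this analysis supports it.

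The cost is a few lines of text, one extra analysis, and extraction of doses that should already be charted. No dose, sample size or clinical rule changes. The conversions are approximate, more so because the Background cites up to a 17-fold variation in methadone blood concentration at a given dose, so the result should be shown as a range. The opioid-sparing claim may also become less favourable.

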The patients will be randomized with 1:1 ratio of intervention and control groups, in blinded blocks of 5, randomly assigned by software used on www.randomizer.org to create 60 study patients and 60 control patients. Envelopes will be used to assign the patients in blocks of 5. Therefore in the first group is to be a control group, the first 5 patients will be controls, then the next group of 5 will be randomly assigned to control or intervention group based on a randomized protocol listed on a study envelope. Overall the blocks of 5 will create even groups of control and intervention patients overall to reach the 120 patient goal. One member of the study team, not involved in the surgical procedure and post-operative pain evaluation will be designated unblended and will communicate with the anesthesiology team pre-operatively to determine whether the patient is to receive methadone or not. The anesthesia team will be responsible for allocation and administration of the methadone, in addition to the standard fentanyl and ketamine, from the Montefiore pharmacy which is already available for intra-operative use as an alternate narcotic regimen. Post-operatively, blinded team members will collect pain data, as well as time to ambulation and discharge data. The pain measures will be patient derived, and time to event data will be part of the patient's chart.

Describe what safety outcomes will be monitored

Safety outcomes to be measured as stated in the adverse events section of this protocol include risks of using any opioid narcotic, which include overdose leading to respiratory depression, dependence and QTc prolongation. Psychological risks include obtunded, lethargic state or altered mental status due to long half-life and opioid effects post-operatively and any resultant mental distress, especially in opioid-naïve patients

Include a data safety monitoring plan

A data safety monitoring plan is included in section 7, under the subheading "Describe methods for interim analyses or early stopping, if applicable"

➤ For Observational studies

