 We proposed to recruit 60 patients to undergo the new treatment and another 60 as controls. This gives us greater than 80% (95%) power to detect an improvement of 0.56 (0.74) within-group standard deviation at statistical significance level 0.05 as had been calculated to be 51 patients per group. Using 60 patients will ensure the usability of our data to detect differences of this effect sizes between groups. From our preliminary data, the standard deviation of time to discharge is 6.7 days, therefore, our sample size is able to detect an average reduction of 3.8 days (5.0 days) in time to discharge with 80% (95%) power.

Describe methods for interim analyses or early stopping, if applicable A data safety monitoring committee will be organized for the purposes of data evaluation in this study.

The members of the committee will include [name], neurosurgeon in the Department of Neurosurgery who performs spinal surgeries yet is not involved in the implementation of this project, and [name], statistician in the Department of Epidemiology and Population Health who is not involved in this protocol. After 20 patients complete the study (approximately 10 patients in each arm), interim analyses will be performed to compare pain ratings, narcotic usage, time to ambulation, and time to discharge to control patients, and the data safety monitoring committee will be asked to review all results and advise the study personnel as well as the IRB about study continuation. If there a significant increase in any of these measured values beyond a single standard deviation of the mean, the data safety monitoring committee and the IRB will come to a decision regarding continuation of the study. Assuming the outcome follows a normal distribution, with 10 patients in each arm, and under the null hypothesis that there is no difference between two groups, the chance of observing a difference greater than or equal to one standard deviation between two groups is about 1/100000. With four measures considered here, the overall Type I error will be no greater than 5/100000. Therefore, the loss of power from the

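### Time to first ambulation is to be tested in days, with no time origin or rounding rule; whole-day scoring would discard information and could break the outlier rule

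*Combined protocol and SAP*

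**What the plan says.** The title is "Single-dose Intraoperative Methadone for Early Ambulation and Sustained Pain Control in Spinal Fusion Surgery Patients". Section 2, under primary and secondary outcomes, lists "the time to first ambulation after surgery with PT" among several primary outcomes, without a unit. Section 7a, answering what data will test the hypothesis, gives "days until patients ambulate with physical therapy", taken from the medical record, and applies the two-sample t-test to it.

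The same section opens with "Two sample T-tests will be performed to evaluate continuous variables such a total morphine dose" and includes time to ambulation in that list. It also defines an outlier as a value more than five MADs from the median. Outliers can prompt a switch to the Wilcoxon test, and flagged patients may be excluded after review.

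On the source, section 2 (randomization and blinding) says that "time to event data will be part of the patient's chart". The power statement in section 7a is generic: "greater than 80% (95%) power to detect an improvement of 0.56 (0.74) within-group standard deviation". Its only worked example is time to discharge, with an SD of 6.7 days. No mean or SD is given for time to ambulation.

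**The concern.** First ambulation after a one- or two-level fusion probably falls within the first few days (an assumption; the documents do not say). A whole-day count would then take only a few values. A calendar-day count also depends on the hour at which surgery ended, which has nothing to do with treatment. Both add noise to an outcome the trial is named for, and a gain of several hours could be missed.

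There is a second consequence. The 5-MAD rule presumes a variable with spread around its median. A day count with one dominant value has none, so the rule could open many ordinary patients to review and possible exclusion.

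**Working it through.** **1. The plan's own figures.** Inputs from section 7a: "We proposed to recruit 60 patients to undergo the new treatment and another 60 as controls", effect sizes 0.56 and 0.74 SD, significance level 0.05, 51 calculated per group. Two-sided noncentral t:
- 51 per group, 0.56 SD: 80.0%. The stated 51 reproduces.
- 60 per group: 86.0% at 0.56 SD and 98.0% at 0.74 SD, consistent with the plan's claim.

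**2. Whole days, by approximation.** Rounding to 24 h cells adds variance of about 24²/12 = 48 h². The effective effect is d = 0.56/√(1 + 48/SD²). For SD 8 h: 48/64 = 0.75 and 0.56/√1.75 = 0.423. For SD 24 h: 48/576 = 0.083 and 0.56/√1.083 = 0.538.

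| Assumed SD (h) | Power in whole days | Loss from 86.0% |
|---|---|---|
| 6 | 51.3% | 34.7 |
| 8 | 63.3% | 22.7 |
| 10 | 70.6% | 15.4 |
| 12 | 75.0% | 11.0 |
| 18 | 81.0% | 5.0 |
| 24 | 83.2% | 2.8 |
| 36 | 84.8% | 1.2 |

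**3. Simulation, walking possible at any hour.** Assumptions: log-normal times, surgery ending 11:00-18:00, calendar-day scoring, 60 per arm.
- Mean 24 h, SD 10 h, 5 h gain. With equal SDs, d = 5/10 = 0.50: 78% in hours, about 58% in days. If the treated SD shrinks with its mean, it is 10 × 19/24 = 7.9 h. The pooled SD is √((100 + 62.7)/2) = 9.02 h and d = 5/9.02 = 0.55: 86% in hours, about 58% in days.
- Mean 30 h, SD 12 h, 6 h gain: 78% v 53% with equal SDs, 86% v 66% with a proportional SD.
- Mean 36 h, SD 24 h, 12 h gain: 78% v 78% with equal SDs, 91% v 87% with a proportional SD.

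Across SDs of 8-12 h the loss is roughly 12-36 points in most settings. That range is not a bound. With gamma times, mean 20 h and a 0.56 SD effect, the loss ran from 1 point (SD 12 h, calendar days: 82.9% to 81.9%) to 44 points (SD 10 h, completed 24 h days: 85.6% to 41.4%).

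**4. Walks only in therapy hours.** The outcome is ambulation with PT, so suppose walks occur only between 08:00 and 16:00 (an assumption). At SDs of 8-12 h, if patients who become ready out of hours walk when the next session opens, hours gain about 3-15 points over calendar days. If they instead walk at some point during the next session, the gain nearly vanishes: 65% v 65%, 76% v 74% and 88% v 88% in the three scenarios with a proportional SD.

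**5. The outlier rule.** If more than half of patients share one day value, that value is the median and more than half of the absolute deviations are zero. So MAD = 0 and 5 × MAD = 0, and every patient on any other day is flagged. In the step 3 proportional-SD scenarios the commonest day held 82%, 68% and 54% of control patients.

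**6. Time to discharge, for comparison.** SD 6.7 × 24 = 160.8 h, and 48/160.8² = 0.0019. Power moves from 86.04% to 85.98%.

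**The case against.** Days may be no more than a unit. Section 7a calls the variable continuous, and its discharge example uses decimal days (3.8 days). Decimal days lose nothing. This stands to the extent that whole-day scoring is an inference. But no section says which is meant, and someone abstracting from the current wording could well record postoperative day 0, 1 or 2.

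The stronger objection is that therapists work in daytime sessions, so the calendar day may already hold nearly all the usable information. This also stands: step 4 shows the gain from hours can be near zero. Nor do hours win in every simulated setting. With gamma times at mean 36 h and SD 36 h, power was 67.9% in hours and 71.4% in calendar days.

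Two inferences go too far. A reader might take "time to event data will be part of the" patient's chart to mean that clock times of walking are recorded. The sentence does not say so, and this must be checked. A reader might also extend the point to time to discharge, but step 6 shows rounding is negligible there.

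Finally, a flag under the 5-MAD rule is not automatic exclusion, because review follows. That limits the harm but leaves the rule unable to identify unusual patients.

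**Conclusion.** The measure is under-defined: the unit is days, with neither an origin nor a counting rule, for a title and primary outcome that the plan treats as continuous. If it is scored in whole days with an SD of about 8-12 h, the loss is roughly 12-36 points when walking can occur at any hour. It is about 3-15 points, possibly close to none, when walking is confined to therapy hours. With an SD of a day or more, the approximation and most calendar-day settings lose about 1-6 points. Counting completed 24 h days can cost more when the mean is short: 82.1% to 72.3% with normal times at mean 24 h and SD 24 h.

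A reader might conclude that the trial has only about 60% power for ambulation. The documents do not support that. By the approximation, 60% at 0.56 SD needs an SD near 7.3 h, no ambulation SD is given, and the 0.56 SD effect is not specific to ambulation. The outlier problem does not depend on the size of the power loss, only on whether one day value covers more than half of patients.

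**What to change.** In section 7a, define the outcome as elapsed hours from end of surgery to first ambulation with PT, using the charted time. First confirm that the chart records that time. If it does not, arrange for it to be recorded before enrolment, since a missing time cannot be recovered later. If only dates can be had, state how days are counted and do not apply the 5-MAD rule to this variable. Leave time to discharge as it is.

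The cost is a line of wording, the check of the chart, and abstracting a time instead of a date. No patients or visits are added.
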